However, few studies on BC screening have focused specifically on barriers/facilitators of breast MRI in high risk populations. Screening breast MRI is unique for three reasons. First, it is a supplemental procedure, to be done in addition to annual mammograms. Women who are adherent to mammography screening still have low rates of screening breast MRI.⁴⁵ Thus, the barriers to breast MRI are ones that do not prevent women from receiving mammograms. Second, screening breast MRI is only recommended for women with high BC risk. These women may differ significantly from the general population in terms of HSUM factors, including predisposing factors, enabling factors, and perceived need. Finally, the scant literature on screening breast MRI demonstrates unique features of the MRI procedure itself that may impact utilization, including medical contraindications, fewer MRI facilities, and significantly greater costs.^{10,18,19} Furthermore, existing studies are limited; they are retrospective in nature and include homogeneous populations.

This project is based on rigorous prior research demonstrating (a) established risk factors for BC,²²⁻²⁵ (b) a proven modality for screening this population (e.g., breast MRI),⁶ and (c) under-utilization of screening breast MRI in women at high BC risk.^{7,11} Thus, we propose a descriptive, cross-sectional, mixed-methods study of barriers to screening breast MRI utilization among high risk women. Guided by

the HSUM, we will conduct a comprehensive quantitative and qualitative assessment of barriers to MRI utilization. In Aim 1, community-based high risk women (N=300) will be surveyed regarding HSUM factors and breast MRI utilization. Results will identify patient-level HSUM factors significantly associated with screening outcomes. In Aim 2, a subset of Aim 1 patients (N=30), will complete semi-structured interviews to identify gaps in our theoretical conceptualization of breast MRI utilization. Successful completion of this study will provide an explanatory framework for screening breast MRI utilization. This explanatory framework will inform our program of research, ultimately leading to the development and testing of a community-based, multilevel intervention incorporating individual (e.g., education, motivational interviewing), provider (e.g., education, reminders/notifications), and/or systems-level (e.g., patient navigation, screening voucher) components.

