C.3.b Screening Behaviors in High Risk BC Survivors Following Genetic Testing. [name] recently completed an ACS funded grant to examine the impact of genetic counseling/testing on BC recurrence risk management behaviors among Black women with invasive BC diagnosed age ≤ 50 years prospectively recruited via the Florida Cancer Data System. One year after genetic testing, 50% had not received a physician recommendation for breast MRI and only 33% received breast MRI in the past 12 months.⁴⁵ Further, *BRCA1/2* status was unrelated to MRI receipt (30% positive v. 33% negative/variant of uncertain significance; $p=0.85$).

C.3.c Screening Behaviors in Unaffected High Risk Women Following Risk Notification. In 2017, our team conducted a pilot study of risk-management behaviors among women presenting for routine mammography.⁴⁷ Of 66 high risk women, 80% had not received a physician recommendation for breast MRI 6-months post-mammography; only 8% had received screening breast MRI. Of those who obtained a breast MRI (n=6), 4 (67%) indicated that they did so because of a physician recommendation.

C.3.d Summary. Findings support the need for additional research to assess barriers/facilitators of screening breast MRI.

C.4 Study Design and Methods.

We apply a sequential mixed methods design (Table 1);⁴⁸ the quantitative aim is implemented first, and the qualitative aim that follows is used to explain/extend the quantitative findings. The integration of qualitative and quantitative will occur at two time points: (1) Aim 1 quantitative data will be used to selectively sample participants and design interview guides for Aim 2; and (2) in final data interpretation.

Table 1. Study Design.

Strategy/Aim	Sample	Goals	Analysis
Phase I (QUAN): Survey Methodology Aim 1. To assess HSUM factors influencing screening breast MRI utilization.	Convenience sample of 150 women with high ($\geq 20\%$) lifetime BC risk (n=50 non-Hispanic White, n=50 non-Hispanic Black, n=50 Latina).	Identify levels of influence and specific predictors of screening breast MRI.	Descriptive statistics Logistic regression
Phase II (qual): In-depth Individual Interviews Aim 2. To confirm, refine, or expand our conceptual model of screening breast MRI utilization.	Purposive sampling of 30 women from Aim 1, selected based on expected/actual MRI receipt.	Identify gaps in our theoretical conceptualization of breast MRI utilization	Content analysis

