C.4.a Aim 1 Overview. The survey employed in this aim will be based on the HSUM and iteratively revised based on CAB feedback. Measures will be selected and adapted for relevance to MRI screening; potential measures are listed below (Section C.4.a.4). The Moffitt Cancer Center (MCC) Population Research, Interventions, and Measurement (PRISM) Core will assist with survey design and production. The PRISM Core has expertise in developing surveys that are acceptable and easy-to-understand, which subsequently enhances the quality of survey data.⁴⁹ The resulting survey will assess predisposing factors, enabling factors, perceived need, and health behaviors. The goal is to inform future intervention studies addressing patient barriers to screening breast MRI.

C.4.a.1 Aim 1 Inclusion/Exclusion Criteria. Biological females; able to speak/read English; within 2 years of last screening mammogram. Women will self-report *BRCA1/2* status; women with a pathogenic *BRCA1/2* mutation are eligible. Non-carriers, women with a variant of uncertain significance, and women with unknown carrier status will then be screened for lifetime BC risk using the National Cancer Institute (NCI) Breast Cancer Risk Assessment Tool (BCRAT).²⁶ For the proposed study, women with estimated lifetime risk $\geq 20\%$ will be eligible. We will exclude women with a prior diagnosis of BC.

The inclusion criterion of age will vary based on *BRCA1/2* status. For women with a pathogenic *BRCA1/2* mutation, women ages 25-85 will be eligible, as breast MRI screening is recommended to be initiated at age 25 for this population. For women without a pathogenic *BRCA1/2* mutation, women ages 35-85 will be eligible.

C.4.a.2 Aim 1 Ascertainment and Enrollment. To enroll 300 participants, we will use five different recruitment strategies.

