TDM to distribute the survey. We will use the following approach: (1) mailed packet including a cover letter, two copies of the informed consent form, paper survey, URL for the web-based survey, and postage paid return envelope; (2) 1st thank you/reminder postcard; (3) replacement survey; (4) 2nd thank you/reminder postcard; and (5) a final survey with a letter stating a final date for survey submission. Materials will be mailed every 2 weeks.

Upon completion, all survey respondents will receive a \$10 gift card.

C.4.a.4 Aim 1 Measures. Predisposing factors: Sociodemographics, medical contraindications for MRI, BC Awareness Scale,⁶⁰ Multidimensional Health Locus of Control Scale⁶¹ and Medical Outcomes Study 12-Item Short Form Health Survey (SF-12)⁶². Enabling factors: Medical Outcomes Study Social Support Survey,⁶³ cost/insurance factors (employment, income, insurance), site of care, access to on-site MRI, and travel time to site of care. Perceived need: Perceived susceptibility,⁶⁴ perceived norms,⁶⁵ provider recommendation for screening, and attitudes towards screening.⁴⁶ Health Behaviors: Patient-reported receipt of BC screening (mammogram, ultrasound, and MRI) and other BC risk management behaviors (chemoprevention, genetic counseling/testing) in the last 12 months.

C.4.a.5 Aim 1 Analytic Approach.

Data Management and Analysis: We will calculate descriptive statistics for predisposing factors, enabling factors, perceived need and health behaviors. We will use multivariable logistic regression to estimate odds ratios (ORs) for the relationships of the HSUM predictors with health behaviors. In the event that data is missing, we will use multiple imputation (with data assumed to be missing at random) to assess the robustness of results based on participants with complete data. We will account for site of recruitment (e.g., MCC or LCCC) in all analyses.

Sample Size: With N=300, we will have >80% power for multivariable logistic regression examining ORs at $\alpha=0.05$ (two-tailed). We can detect OR=1.8 when the predictor (X) is continuous and normally distributed, the probability of screening at the mean of X is 0.2, and the coefficient of determination between X and a continuous covariate (Z) is 0.05. When X and Z are binary with 50% and 25% prevalence, respectively, we will have 75% power to detect OR=2.5, when the probability of screening is 0.25 when X=0 and Z=0.

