Expected Outcomes: We expect to identify 2-4 most influential HSUM factors. We will also quantify the effect size, enabling appropriate powering of a future RCT. In line with our sequential mixed-methods design, Aim 1 data will inform Aim 2 interviews.

Figure 2. Sample Composition.

[figure not shown]

Table 2. Operational Definitions of HSUM Factors.

HSUM Factors	Definition	Operational Definition
Predisposing Factors	Socio-cultural characteristics of individuals	High: ≥ 3 of the following: (1) High BC awareness (median split); (2) Low fatalism (median split); (3) Low BC worry (median split); (4) Low depression (median split); (5) Low anxiety (median split).
Enabling Factors	Logistical aspects of obtaining care	High: ≥ 3 of the following: (1) High social support (median split); (2) Household income above poverty line (yes); (3) Insured (yes); (4) MRI at usual site of care (yes); (5) Travel time to closest MRI facility (≤ 30 minutes).
Perceived Need	How women view their need for breast MRI	High: ≥ 2 of the following: (1) High perceived BC susceptibility (median split); (2) High perceived norms for BC screening (median split); (3) Provider recommendation for screening (yes); (4) More positive attitudes towards screening (median split).

C.4.b Aim 2 Overview. We will conduct semi-structured qualitative interviews with a sub-sample of Aim 1 participants (N=30). We will select information-rich cases from Aim 1 for in-depth qualitative analysis in Aim 2 (Figure 3). To do so, we will categorize Aim 1 participants based on expected and actual MRI receipt (see C.4.b.1). From participants in each group, we will gather in-depth information about their breast MRI screening decisions. The goals of Aim 2 are to (a) obtain an in-depth understanding of barriers/facilitators to MRI from the patient perspective, and (b) identify gaps in our theoretical conceptualization of breast MRI utilization.

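### The 75% power stated for OR=2.5 at N=300 does not follow from its own inputs (about 93–96%; 75% fits roughly 150 women), and Table 1 gives 150 women where the rest of the text gives 300

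*Combined protocol and SAP*

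**What the plan says.** The Sample Size paragraph of C.4.a.5 begins: "With N=300, we will have >80% power for multivariable logistic regression", at alpha 0.05, two-tailed. It gives two scenarios and names no other sample size.

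- Continuous predictor: "We can detect OR=1.8 when the predictor (X) is continuous and normally distributed", with screening probability 0.2 at the mean of X and a coefficient of determination of 0.05 between X and a continuous covariate Z.
- Binary predictor, with X and Z at 50% and 25% prevalence: "we will have 75% power to detect OR=2.5, when the probability of screening is 0.25 when X=0 and Z=0".

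The enrolment target is 300 in the Aim 1 statement, in Section B ("In Aim 1, community-based high risk women (N=300) will be surveyed"), in C.4.a.2 ("To enroll 300 participants, we will use five different recruitment strategies"), and in D.1.a, D.1.b and D.2.a. Table 1 in C.4 instead describes the Aim 1 convenience sample as "of 150 women with high" lifetime risk, divided as "n=50 non-Hispanic White, n=50 non-Hispanic Black, n=50 Latina".

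Under Expected Outcomes in C.4.a.5 the plan adds: "We will also quantify the effect size, enabling appropriate powering of a future RCT".

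**The concern.** The paragraph claims more than 80% power and then 75%, for the same N, alpha and type of model. Reading the figure of more than 80% as covering only the continuous scenario removes that contradiction. It does not explain why a two-and-a-half-fold odds ratio for an evenly split predictor should have only 75% power with 300 women.

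This paragraph is the only quantitative justification of the Aim 1 sample size. Several of the factors under study are binary (provider recommendation, insurance, on-site MRI), so the binary scenario applies to hypothesised predictors. A reader should be able to see which effects the survey can reliably detect, especially since the results are meant to help power a later trial.

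Table 1 raises a separate problem: it halves the enrolment target. Its 50/50/50 split, the only racial/ethnic allocation in the visible text, sums to 150.

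**Working it through.** **Inputs from C.4.a.5.** N=300; two-sided alpha 0.05 (z=1.96). Binary scenario: X prevalence 0.5, Z prevalence 0.25, P=0.25 at X=0 and Z=0, OR=2.5. Continuous scenario: P=0.2 at mean X, R²=0.05, OR=1.8.

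**Assumptions not in the documents.** The Z–outcome OR and the X–Z OR (both varied below); OR=1.8 taken per standard deviation; all surveys analysable.

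**Binary predictor, Z unrelated to outcome and to X.**

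- Odds at X=1 are (0.25/0.75) × 2.5 = 0.833, so P=0.4545.
- p(1−p) is 0.1875 at X=0 and 0.2479 at X=1.
- The variance of the log OR is 1/(n₀ × 0.1875) + 1/(n₁ × 0.2479), with n₀ = n₁ = N/2.
- Wald power is Φ(ln 2.5/SE − 1.96), with ln 2.5 = 0.9163.

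| N | SE | ln 2.5/SE | Power |
|---|---|---|---|
| 300 | 0.2499 | 3.667 | Φ(1.707) = 95.6% |
| 150 | 0.3534 | 2.593 | Φ(0.633) = 73.7% |

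The stated 75% is not reproduced at N=300 but nearly is at N=150. Solving for 75% power: N = (1.96 + 0.6745)² × 18.73/0.9163² = 155, where 18.73 is the variance multiplied by N.

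**Varying the unstated Z associations.** The same calculation used the full Fisher information over the four X-by-Z cells, with Z–outcome OR 0.5 to 3 and X–Z OR 0.5 to 3.

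- N=300: 93.3–96.1%.
- N=150: 68.6–74.8%.
- N giving 75% power: about 151–174.
- OR with 80% power at N=300: 2.00–2.11.
- Both associations at the extreme value of 0.1, N=300: still 87%.

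**Cross-checks.**

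- A two-proportion calculation ignoring Z gives 96.3% at N=300 and 75.1% at N=150.
- Simulation of the logistic model gives 96.2% and 96.6% at N=300, and 74.8% and 75.2% at N=150 (Z–outcome OR 1 and 2, 6,000 runs each).
- Unusable surveys do not close the gap: with no Z associations, 270 analysable surveys give 93.6% and 250 give 91.7%.
- Other readings at N=300 also miss 75%: one-sided test 98%; alpha 0.01, 86–87%; alpha 0.005, 81–82%; prevalences of X and Z swapped, 85–91%; protective OR of 1/2.5, 79–87%; X-by-Z interaction OR of 2.5, 31–36%.

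**Continuous predictor.** The Hsieh–Bloch–Larsen formula gives N = (1.96 + 0.8416)²/[0.2 × 0.8 × (ln 1.8)² × 0.95] = 7.849/0.0525 = 149.5 for 80% power. Across methods:

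| Method | Power, N=150 | Power, N=300 | OR with 80% power, N=300 |
|---|---|---|---|
| Hsieh–Bloch–Larsen | 80.1% | 97.8% | 1.51 |
| Wald, Fisher information (no Z effect) | 75.7% | 96.4% | 1.53 |
| Hsieh 1989 | 70.3% | 94.9% | 1.57 |
| Simulation | 76.8% | 97.2% | not computed |

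**Table 1.** 50 + 50 + 50 = 150, half of 300.

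**The case against.** The strongest reply is that little depends on this. The error is conservative: with 300 surveys the study has more power than it claims, and this is a one-time, minimal-risk, descriptive survey. That is right, and it limits the severity.

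The OR=1.8 sentence is not false, since power there does exceed 80%. That also stands. The comment is only that 1.8 is not the smallest effect detectable at N=300. Confidence intervals will carry most of the interpretation of a null result, so the detectable OR is an aid to reading one rather than a necessity.

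The link to N=150 is firmer for the binary scenario than for the continuous one, where only one of three formulas reaches 80% at 150. That the figures were carried over from a 150-woman design is an inference; the documents do not say so.

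Figure 2, titled Sample Composition, is not shown and may give a racial/ethnic breakdown. It could not make Table 1's 150 equal 300.

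The most useful caution concerns the replacement figures. They belong to the paragraph's one-covariate scenario, whereas the analysis plans many predictors plus site. As an illustration, an R² of 0.4 between X and the other covariates takes 95.6% to Φ(3.667 × √0.6 − 1.96) = 81%, and an R² of 0.5 takes it to 74%. The inputs also imply about 35% overall uptake, (0.25 + 0.4545)/2, against the 25% minimum monitored under C.4.a.2. At 25% overall uptake, power is about 91%. With P=0.08 at X=0 and Z=0 (8% was the uptake in the C.3.c pilot), it is about 70%. None of this rescues the stated 75%, which is tied to explicit inputs, but the corrected figures should be printed with their conditions.

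**Conclusion.** The concern holds. On the paragraph's own inputs, power for OR=2.5 at N=300 is about 93–96%, not 75%, an understatement of about 18–21 points. This assumes Z–outcome and X–Z ORs between 0.5 and 3 and 300 analysable surveys; extreme associations still leave 87%. The OR=1.8 statement is true at N=300 (about 95–98%, taking the OR per standard deviation) but is not the detectable effect for that N. Separately, and whatever the power calculation, Table 1 contradicts the enrolment target given everywhere else. This should be fixed, but it does not threaten the study: if 300 surveys are analysed, the design is stronger than stated under its own inputs.

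**What to change.** 1. Confirm the Aim 1 sample size, which is 300 by all the text outside Table 1, and make Table 1 agree, including its racial/ethnic composition. The investigators must decide that composition, and it may affect recruitment targets.
2. Restate power for the confirmed N. At 300 the paragraph could read: with 300 analysable surveys, two-sided alpha 0.05 and one covariate as specified, power is about 95–98% for OR=1.8 per standard deviation of a continuous predictor (80% for OR about 1.5), and about 93–96% for OR=2.5 for a binary predictor (80% for OR about 2.0).
3. State the assumed Z–outcome and X–Z associations, the unit of the continuous OR, and the formula or software. Say that the figures apply to a single covariate, and preferably add one line showing how they fall with the larger planned covariate set or lower uptake.

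The cost is one paragraph and one table entry, plus the composition decision. No additional participants are needed.

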Breast MRI is underutilized among high risk women.^{7,11} Among identified *BRCA1/2* carriers – a very select subpopulation of high risk women receiving personalized genetic risk information and screening recommendations – uptake of breast MRI is significantly lower than other breast screening options (e.g., 24-48% versus 43-82% for annual mammography).¹¹⁻¹³ Women at elevated risk for other reasons are even less likely to receive breast MRI: estimated uptake of MRI in the overall population of high risk women ranges from 1-7%.⁷⁻¹¹ Thus, efforts are needed to ensure risk-appropriate utilization of breast MRI.

The proposed research is theoretically driven. The **Health Services Utilization Model** (HSUM; Figure 1)²¹ states that health-related service use is a function of an individual's predisposing factors, enabling factors, and perceived need. Our team has successfully used this model in prior studies^{31,32} and we will adapt it to reflect constructs important to screening breast MRI.

Figure 1. Theoretical Model.

Prior research has demonstrated that patient-level barriers to BC screening in the general population exist at each of the HSUM levels. Predisposing factors associated with lower screening rates include less knowledge about BC and certain health/cultural beliefs (i.e., higher fatalism).³³⁻³⁵ Data suggest a curvilinear relationship between screening and anxiety; adherence improves with increasing anxiety until the anxiety becomes too intense, resulting in avoidance.³⁶⁻³⁸ Enabling factors such as more social support, lower cost/better insurance coverage, and greater access to care significantly predict higher screening rates.^{34,39-42} Finally, BC screening may be influenced by perceived need, a social phenomenon that includes perceived susceptibility to BC, social norms (e.g., others' expectations for screening and one's willingness to adhere to these expectations), provider recommendation for screening, and attitudes towards screening; lower perceived need may deter utilization.^{43,44}

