Fourth, we will partner with the group Facing Our Risk of Cancer Empowered (FORCE) to advertise the study on their e-mail list. FORCE is a non-profit organization with the mission of improving the lives of individuals and families affected by hereditary breast, ovarian, and related cancers. The FORCE e-mail list is comprised of men and women with an interest in issues related to hereditary breast and ovarian cancer. E-mail advertisements will describe the study and include contact information for study staff. Potential participants will contact study staff via phone or e-mail, be assessed for eligibility, confirm their mailing address or e-mail address, and be sent the survey as described below. Informed consent will be documented on forms mailed and returned with the survey or via electronic signature on web-based forms, as preferred.

Finally, we will advertise the study using flyers placed in mammography and primary care clinics and distributed by the Moffitt Program for Outreach Wellness Education and Resources (M-POWER) at community outreach events. Flyers will include a brief description of the study and contact information for study staff. Potential participants will contact study staff via phone or e-mail, be assessed for eligibility, confirm their mailing address or e-mail address, and be sent the survey as described below. Informed consent will be documented on forms mailed and returned with the survey or via electronic signature on web-based forms, as preferred.

We will monitor survey responses to ensure adequate representation ($\geq 25\%$) of women reporting MRI receipt. If we are not on track for adequate accrual by 4 months, we will employ purposive sampling through the MCC high risk breast clinic, where screening MRI is standard.

C.4.a.3 Aim 1 Assessment Procedures. Assessment procedures will vary based on recruitment strategy.

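### The Aim 1 power figures match N=150, not the planned 300, and assume one MRI rate for a sample the plan may build by mixing low- and high-uptake sources

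*Combined protocol and SAP*

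**What the plan says.** C.4.a.5 (Sample Size) opens: "With N=300, we will have >80% power for multivariable logistic regression examining ORs at" a two-sided 5% level. It then gives two cases.

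- **Continuous predictor.** "We can detect OR=1.8 when the predictor (X) is continuous and normally distributed", where "the probability of screening at the mean of X is 0.2" and the R-squared of X with a covariate Z is 0.05.
- **Binary predictor.** X has 50% prevalence and Z 25%, and "we will have 75% power to detect OR=2.5, when the probability of screening is 0.25 when X=0 and Z=0".

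Table 1 (C.4) still describes the Aim 1 sample as 150 women, 50 in each of three racial and ethnic groups.

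On uptake, section B says "estimated uptake of MRI in the overall population of high risk women ranges from 1-7" per cent, and gives 24-48% for identified BRCA1/2 carriers. In the team's mammography pilot (C.3.c), "only 8% had received screening breast MRI" at six months. Carriers are eligible, and a hereditary-cancer e-mail list is one of five recruitment routes; no expected share is given for any route.

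C.4.a.2 sets a floor of 25% reporting MRI. If accrual is off track at four months, "we will employ purposive sampling through the MCC high risk breast clinic, where screening MRI is standard". The clinic's MRI rate is not stated. C.4.a.5 adjusts all analyses for site (MCC or LCCC) and does not mention recruitment source.

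**The concern.** A power statement should describe the sample that will be analysed. This one appears not to, in two ways. The figures do not follow from N=300. They also treat the women as one population with a 20-25% chance of MRI, while the plan's uptake figures and its top-up rule point to a mixture of low- and high-uptake sources.

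The second matters most if the top-up is used. Receipt would then depend strongly on where a woman was recruited, and site captures this only partly, because top-up women are all MCC but MCC also recruits through community routes. Leaving out a strong predictor of receipt pulls the other odds ratios toward 1, even for factors unrelated to it. C.4.a.5 expects Aim 1 to identify the 2-4 most influential factors and to supply effect sizes for powering a later trial. Both uses suffer if ORs are diluted by an amount that depends on how many clinic women were added.

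**Working it through.** **1. The plan's own figures.** Inputs from C.4.a.5.

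*Binary X.* Odds at X=0 are 0.25/0.75 = 0.333; times 2.5 gives 0.833, so p1 = 0.4545. The difference is 0.2045 and the mean rate 0.3523. With n per X group,

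z = [0.2045·√n − 1.96·√(2·0.3523·0.6477)] / √(0.25·0.75 + 0.4545·0.5455) = (0.2045·√n − 1.324) / 0.660.

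- N=300 (n=150): z = 1.79, power 96.3%.
- N=150 (n=75): z = 0.68, power 75.1%.

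A Wald calculation with Z in the model gives 93.7-96.1% at N=300 (odds ratios for Z from 0.4 to 3). One-sided testing, 25% prevalence of X, a protective OR of 1/2.5 and an X-by-Z term give 84.5-98.3% at N=300, so none yields 75%.

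*Continuous X* (OR taken per SD). Power = Φ(√(N·p(1−p)·(ln 1.8)²·(1−0.05)) − 1.96), with p=0.20.

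- N=300: Φ(3.97 − 1.96) = 97.8%.
- N=150: Φ(2.81 − 1.96) = 80.1%.

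**2. Can community routes reach 25% without the clinic?** With carrier share c and carrier uptake at the top of its range, 0.08(1−c) + 0.48c = 0.25 gives c = 0.425; using 7% for the others gives 0.44. At 24% carrier uptake, 25% is never reached.

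**3. Size of the top-up.** Clinic women needed = 300·(0.25 − 0.08)/(m − 0.08), where m is the clinic rate. This is about 128, 98, 76 and 62 for m = 48%, 60%, 75% and 90%. All four rates are assumptions; 48% borrows the top of the carrier range.

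**4. Information in the mixture.** Information on a log OR estimated within source is roughly proportional to the sum of n·p(1−p).

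- Uniform 25%: 300·0.1875 = 56.3.
- 8%/48%: 172·0.0736 + 128·0.2496 = 44.6 (79% of uniform).
- 8%/60%: 202·0.0736 + 98·0.24 = 38.4 (68%).
- 8%/75%: 224·0.0736 + 76·0.1875 = 30.7 (55%).
- 8%/90%: 238·0.0736 + 62·0.09 = 23.1 (41%).

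**5. Simulated power, binary X, true OR 2.5 in both sources, N=300.** Likelihood-ratio test at two-sided 0.05, X independent of source, clinic women all MCC, others split evenly by site, 2,000 replicates (Monte Carlo error about ±2 points). The lower power in each range treats 8% and m as overall rates. The higher treats them as X=0 rates, which lifts overall receipt above 25%. For example, at 90% the source averages become 0.929 and 0.129, and (62·0.929 + 238·0.129)/300 = 29%.

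| Clinic rate (assumed) | Power, site only | Estimated OR, site only | Power, site + source |
|---|---|---|---|
| 48% | 77-83% | about 2.1 | 84-89% |
| 60% | 67-70% | 1.9-2.0 | 79-84% |
| 75% | 48-57% | 1.7-1.8 | 68-77% |
| 90% | 29-44% | 1.5-1.6 | 57-71% |

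For continuous X with OR=1.8, site-only power is about 85%, 69% and 46% at clinic rates of 60%, 75% and 90%, and 94%, 89% and 78% with a source term.

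**6. No top-up, uniform 8%.** Continuous: Φ(2.69 − 1.96) = 77%. Binary: 72% if 8% is the X=0 rate, 53% if it is the overall rate.

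**The case against.** A reader might infer that the top-up cannot restore the stated power, or that Aim 1 is underpowered. The documents do not support either.

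- **N=300 leaves slack.** On the plan's convention (rate at X=0), a uniform baseline of about 8.7% is enough for 75% and 80%. The pilot's six receivers among 66 women are 9.1%, which does not match its printed 8%; at 9.1% power is about 77% (binary) and 81% (continuous) with no top-up. The pilot window was six months, while Aim 1 asks about twelve. This stands, although binary power falls below 75% if 9.1% is the overall rate.
- **The clinic rate is unknown.** At 48%, the highest screening-MRI uptake quoted for any high-risk group in section B, the stated 75% is met even with site-only adjustment. This stands, and the conclusion must be conditional.
- **1-8% is not the planned sample's rate.** Carriers are eligible and actively sought. With about 43-44% carriers at 48% uptake and no top-up, binary power is about 79% with site only. This stands too; the pre-top-up rate is unknown.
- **The fitted model may hold more than site.** C.4.a.4 lists site of care, access to on-site MRI and provider recommendation, which could absorb part of a clinic effect. Independence of X from source is also implausible for those factors. This stands in part: the plan does not say which predictors enter together, and the table applies to factors unrelated to source.

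Nor do the documents say that a non-significant factor will be declared uninfluential; that consequence is an inference.

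**Conclusion.** The concern holds in a conditional form. Independently of any assumption about uptake, the stated 75% and 80% agree with N=150 and not with N=300. That they were carried over from the Table 1 sample is the likely explanation, but the documents do not say so. The claim of more than 80% for the continuous case is true at N=300 only as a loose lower bound.

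A 25% receipt rate built from unlike sources always carries less information than the single rate the paragraph assumes, so meeting the floor does not by itself secure the stated power. With 8% community uptake and site-only adjustment, binary power is below 75% at assumed clinic rates of 60-90% and above it at 48%. Leaving source out also pulls a within-source OR of 2.5 down to about 2.1 at a 48% clinic rate and 1.5-1.6 at 90%. A source term recovers much of the power and removes this dilution, though at 90% power stays below 75%. These figures rest on the assumed clinic rate, 8% elsewhere, no separate carrier stratum, and a factor independent of source.

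**What to change.** 1. Reconcile 150 in Table 1 with 300 elsewhere, and recompute the power paragraph for the sample size that stands.
2. Add recruitment source to the Aim 1 logistic models alongside site, at least as high-risk-clinic top-up versus community routes. Source is known for every participant.
3. State a range for the community MRI rate, carrier share and clinic rate. Over that range give power for OR=1.8 and OR=2.5, or the OR detectable with 80% power, from the model to be fitted. Say whether each rate is overall or at X=0.
4. State that reaching the 25% floor does not by itself secure the stated power.

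The cost is a rewritten paragraph, a short simulation and one model term, with no extra participants or procedures. The power statement becomes a range and may look less favourable. The source term may also absorb part of the effect of factors tied to the clinic, such as provider recommendation and on-site MRI, so report those factors with and without it.
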